### **5.3.10     *Treatment of Acute Rejection***

Prior to initiation of treatment for suspected AR, ensure that:

[figure not shown]
- a) Local blood samples are collected for measurement of serum creatinine concentration, and trough levels of EVL or TAC (if applicable).
- b) Central laboratory samples are collected for immunogenicity, CMV/EBV/BK viral load, IgG & subclasses 1-4 and biomarkers (see [Section 5.6](#)).

The severity of acute rejection will be determined using the 2007 update to the Banff 97 classification, which will also serve as a guide to treatment of any episode that is biopsy confirmed.

Guidelines for the treatment of acute rejection according to the Banff 97 classification and the 2007 update are provided below, in bullets, and in [Figure 5.3.10-1](#) and [Figure 5.3.10-2](#). To the extent clinically feasible, these guidelines are intended to standardize the treatment of acute rejection across clinical sites so as to improve interpretability of data. It is recognized, however, that the guidelines may not be applicable to all clinical situations, such that deviations from them may be required in individual cases. The guidelines are summarized below:

- Subjects with acute rejection of Banff severity grades up to and including IIA should be treated initially with methylprednisolone (as the sodium succinate), 250 - 500 mg i.v. per day for 3 consecutive days. Corticosteroids should then be tapered per investigator's discretion.
- Subjects with acute rejection of Banff severity grades IIB and III should be treated initially with ATGAM, Thymoglobulin, ATG-Fresenius-S, or OKT3. Use of other polyclonal antilymphocyte preparations or polyclonal antithymocyte globulins is permitted in regions where market authorization exists, and if they are indicated for the treatment of acute rejection in kidney transplantation. Use of Campath 1-H is not permitted in this protocol, as it is not indicated for use in kidney transplantation.
- Subjects with acute rejection that is either unresponsive to, or worsening despite initial corticosteroid therapy should have a repeat, percutaneous allograft biopsy performed before initiating treatment for steroid-resistant acute rejection. Subjects may be treated with Thymoglobulin, ATGAM, OKT3, ATG-Fresenius-S, or other approved agents as noted above. Following the last dose of anti-rejection medication, steroids should then be tapered per investigator's discretion.

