#### 8.4.2.1 Acute Rejection

Rates of acute rejection will be summarized by treatment group at Months 6, 12 and 24 using point estimates of the proportion of subjects who have experienced at least one episode of CSBPAR along with the corresponding 95% CIs. Two-sided 95% CIs will be generated for the differences between treatment groups. Descriptive summaries will be provided for the percentages of subjects with CSBPAR in each treatment group, including those for severity grade and treatment received. All grades of acute rejection, excluding those assessed by the pathologist as "borderline changes" (biopsy findings "suspicious" for acute cellular rejection per the Banff criteria), will be included in the analyses of the primary and relevant secondary endpoints for acute rejection. Sensitivity analyses will be performed including acute rejections assessed by the pathologist as "borderline changes" (biopsy findings "suspicious" for acute cellular rejection per the Banff criteria).

The following analyses will provide further understanding regarding the impact of CSBPAR on renal function, graft/subject survival, donor specific antibodies, infection, and malignancy.

- Descriptive summaries of cGFR by treatment group
  - at Month 12 in subjects with and without AR by Month 6 and
  - at Month 24 in subjects with and without AR by Month 12

- Descriptive summaries of graft and subject survival, by treatment group
  - at Month 12 in subjects with and without AR by Month 6 and
  - at Month 24 in subjects with and without AR by Month 12
- Descriptive summaries of infection and malignancy, by treatment group
  - at Month 12 in subjects with and without AR by Month 6 and
  - at Month 24 (by subjects with and without AR by Month 12

In addition, Kaplan-Meier (KM) cumulative event rates will also be performed by treatment groups.

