7 STATISTICAL ANALYSES

7.1 Modifications to the Analyses Specified in the Protocol

Due to the reduction in sample size resulting from premature termination of enrollment as of 31 December 2016, it has been deemed appropriate to revise selected statistical analyses specified in the study protocol [Section 8](#). The following modifications to and clarifications of the analyses have been made:

- 1) All analyses will be performed for the whole study treatment period (i.e. 24 months), including analyses at 6 or 12 months.

- 2) Treatment differences will be produced only for the endpoints specified in the sections of this SAP itemized below, instead for all study endpoints.
- 3) Analysis of acute rejections:
 - a) The treatment differences in the severity grades and therapeutic modalities will not be calculated.
 - b) The sensitivity analyses using the per-protocol population will be performed if there are at least 10% of subjects with a protocol deviation in either treatment groups.
 - c) The sensitivity analyses using the as-treated population will be performed if there are at least 10% of subjects in either treatment group for whom the as-randomized treatment group is different from the as-treated treatment group.
 - d) The sensitivity analysis using right censoring at the time of discontinuation from assigned therapy will not be produced. Acute rejections occurring more than 56 days after the last dose date will be flagged in the listing.
 - e) The descriptive summaries by treatment group for cGFR, graft and subject survival, donor specified antibodies, infection and malignancy at Month 12 for subjects with and without AR by Month 6, and at Month 24 in subjects with and without AR by Month 12, will not be produced. The information regarding these parameters will be included in listings that correspond to the specific analyses of these endpoints.
- 4) Analysis of subject and graft survival:
 - a) A listing including all subjects who died or lost their graft will be produced. Corresponding summaries, treatment differences and time to event analysis will be produced if there are at least 5 subjects across treatment groups who died or experienced graft loss during the 24 Month treatment period.
 - b) Any summaries mentioned above, if to be produced, will only be produced for the whole 24 Month treatment period. The corresponding analyses at 6 and 12 months will not be produced.

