- 9) The summary of median fluorescence intensity (MFI) of anti-HLA donor specific antibodies will not be produced. Instead, the number of subjects with DSA will be summarized.
- 10) Analysis of anti-viral T-cell responses will not be provided. The immune cell phenotypes will be summarized for all subjects and by acute rejection status (subjects experiencing at least one acute rejection vs those without any acute rejection). A corresponding listing will be provided.
- 11) The patterns of protein excretion, by urinary proteomics will be summarized for all subjects and by acute rejection status (subjects experiencing at least one acute rejection vs those without any acute rejection). Proteins that are below LLOQ in more than 50% of samples will not be analyzed. A corresponding listing will be provided.

Due to the fact that some data were not collected, the following analyses cannot be produced:

- 1) Clinically significant changes in vital signs were not collected. Thus, they will not be summarized. Instead, a summary of the number of subjects with systolic or diastolic blood pressure values above the values mentioned in [section 7.6.2.5](#) will be provided. Also, investigators may have reported corresponding adverse events which will be summarized and listed as described in [Section 7.7](#).
- 2) For the analysis of any clinical consequences of CSBPAR, and associated changes in the expression of exploratory gene sets associated with acute rejection, no summary or listing that includes gene expression will be provided.
- 3) The analysis on titers of DSA and of the characterization of any de novo DSA detected by IgM and IgG classes, and by the presence or absence of complement fixing properties will not be produced. Instead, the number of subjects with DSA will be summarized.
- 4) The IHC analyses of any remaining allograft biopsy tissue samples available at sites following clinical review will not be provided, as no such residual tissue samples were submitted for this purpose.

The following analyses will not be provided as part of this analysis plan:

- 1) The analyses related to anti-viral T-cell responses and mean percent change in anti-viral T cell responses will not be produced as part of the analyses described in this analysis plan. If they are to be performed subsequently, they will be described in a separate analysis plan.

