7.6.2 Secondary Endpoints

7.6.2.1 Subject and Graft Survival

A listing will be provided of all subjects who died or experienced graft loss at any time during the study. A listing of all subjects with unknown subject and graft survival status at the end of the 24 month-treatment period will be provided.

If there are at least 5 subjects across treatment groups who died or experienced graft loss during the 24 month-treatment period, the following analyses will be produced:

- The composite endpoints of patient and graft survival at 24 months respectively will be summarized within each treatment groups, using point estimates of the proportion of subjects surviving with a functioning graft, and the corresponding 95% CIs. The point estimate and its 95% CIs will also be generated for the difference between the two treatment regimens.
- The proportion of subjects who die, proportion of subjects who have a graft loss, and the proportion of subjects who experience the following outcomes will each be summarized using point estimates and 95% CI within each treatment group.
 - Overall graft loss rates at 24 months.
 - Rates of death with a functioning graft at 24 months.

- Rates of pure (death-censored) graft loss at 24 months.
- In addition, Kaplan-Meier (KM) estimates of cumulative subject and graft survival rates will also be summarized.
- The subject and allograft survival rates will be summarized among those subjects who did and those who did not experience CSBP. This analysis will be produced only if there are at least 5 subjects across treatment groups who died or experienced graft loss during the 24 month-treatment period.

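### Survival by CSBPAR is grouped on ever versus never rejecting over the same 24 months, which builds immortal-time bias into the table

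*SAP*

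**What the plan says.** SAP 7.6.2.1 gives the analysis as its last bullet: subject and allograft "survival rates will be summarized among those subjects who did and those who did not experience" CSBPAR. Items 4c and 8d of SAP 7.1 repeat it. It is conditional: "If there are at least 5 subjects across treatment groups who died or experienced graft loss during the 24 month-treatment period". Item 4b of SAP 7.1 restricts survival summaries to the full 24 months, and item 1 sets the general frame: "All analyses will be performed for the whole study treatment period (i.e. 24 months), including analyses at 6 or 12 months". The visible text gives no landmark, no time-dependent rejection status and no restriction to subjects still at risk.

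Protocol 8.4.2.1 planned a different set of summaries, including graft and subject survival "at Month 12 in subjects with and without AR by Month 6 and" at Month 24 by rejection by Month 12. Item 3e of SAP 7.1 removes that set, down to the Month 24 part: "at Month 24 in subjects with and without AR by Month 12, will not be produced". The information goes to listings.

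SAP 8.3 adds a rule for unknown survival status. A subject whose status is unknown at Month 12 or 24 counts as a death or graft loss if any of five criteria was met, one of which is an earlier biopsy-proven rejection. Subjects who meet none of the criteria are left out of numerator and denominator.

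**The concern.** The grouping variable is only known after the fact. A subject who dies or loses the graft on Day 20 without having rejected can never enter the CSBPAR group. A subject who first rejects on Day 150 has by definition survived with a graft to Day 150. The CSBPAR group is credited with that guaranteed time, and the other group collects all the losses that precede a rejection. This happens even with complete follow-up.

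The table would be read as evidence on whether rejection under these regimens carries a survival cost. If rejection truly had no effect, this mechanism would show a benefit. If it had a harmful effect, the mechanism would shrink it.

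**Working it through.** **The plan's own figures.** The plan gives no figure for this analysis. Its precision figures for CSBPAR at 35 per arm reproduce and are not in question: 0.2% to 16.4%, 0.1% to 15.1%, and -13.2% to 11.3% for the difference.

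**Inputs from the documents.** 70 subjects; a condition of at least 5 losses (5/70 = 7.1%); a 24-month window; planning CSBPAR rates of 3.8% and 3%. The documents do not give the timing of losses or rejections, so these are assumed and varied.

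**Formula under no effect.** Let S(t) be the probability of being alive with a graft at time t. Let p be the share of subjects who would reject if they stayed at risk, and R the time of that rejection, independent of loss. A subject is observed to reject only if R comes before loss, so P(ever) = p × E[S(R)]. Then:

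- Loss, ever = 1 − S(24) / E[S(R)]
- Loss, never = 1 − (1 − p) × S(24) / (1 − p × E[S(R)])

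**Worked case A.** Constant hazard, S(24) = 65/70 = 0.9286, R uniform over 0–6 months, p = 10%. The cumulative hazard to Month 6 is −ln(0.9286)/4 = 0.01853, so S(6) = 0.9816 and E[S(R)] = (1 − 0.9816)/0.01853 = 0.9908 before rounding.

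- Ever: 1 − 0.9286/0.9908 = 6.3%
- Never: 1 − 0.8357/0.9009 = 7.2%
- Gap: 1.0 point

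| Case (assumed) | E[S(R)] | Loss, ever | Loss, never | Gap (points) |
|---|---|---|---|---|
| A: as above | 0.9908 | 6.3% | 7.2% | 1.0 |
| B: as A, R uniform over 0–24 months | 0.9638 | 3.7% | 7.5% | 3.9 |
| C: 4% lost by Day 30, 6% more by Day 728; R uniform over Days 7–180; p = 10% | 0.9564 | 5.9% | 10.4% | 4.5 |
| D: 15% lost, front-loaded (Weibull shape 0.5); R uniform over 0–24 months; p = 20% | 0.898 | 5.3% | 17.1% | 11.8 |

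Simulation over a wider grid (loss 7.1% or 15%, CSBPAR 3.4% to 20%) gave gaps of 0.9 to 11.8 points, all favouring rejectors.

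**Month 6 landmark restricted to subjects alive with a graft.** Under no effect, later loss is 1 − S(24)/S(6) in both groups: 1 − 0.9286/0.9816 = 5.4% in case A and 1 − 0.9/0.9481 = 5.1% in case C. In simulation, landmark differences stayed within about 0.2 points of zero.

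**The protocol's summaries taken literally.** In case A with S(12) = 0.9636, loss by Month 12 is 1 − 0.9636/0.9908 = 2.7% with rejection by Month 6 and 1 − 0.9 × 0.9636/0.9009 = 3.7% without. The gap is still 1.0 point. Across the scenarios with 10% rejection, the literal wording leaves 0.9 to 7.1 points.

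**The opposing rule in SAP 8.3.** Suppose a share u of each group has unknown status and meets no other criterion. Survival becomes (1 − u) × S(24) in rejectors and stays at S(24) in the rest. With S(24) = 0.9286, u = 5% lowers survival in rejectors by 4.6 points and u = 20% by 18.6 points.

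**Expected group size.** At the planning rates, 35 × 0.038 + 35 × 0.03 = 1.33 + 1.05 = 2.4 rejectors are expected by Month 6. The chance of none is 0.962^35 × 0.97^35 = 8.9%.

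**The case against.** The strongest reply is that little rests on this table. The study is descriptive, no tests are planned, the table appears only with at least 5 losses, and all deaths, graft losses and suspected rejections are listed. With two or three rejectors, one event moves their rate by 33 to 50 points. Even with 7 rejectors, the 4.5-point gap in case C is about 0.3 of one subject. All of this stands and limits the weight of the point. It does not make the grouping right: the table is specified for the situation in which losses occur, which is when it will be read.

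It can also be said that the SAP kept an existing comparison and made it conditional, and did not introduce it in place of the protocol's. Item 8d sits under an endpoint on the consequences of CSBPAR at 6, 12 and 24 months, which supports this. A reader might infer that the protocol had proper landmarks and that dropping them created the bias. The documents do not support that. Protocol 8.4.2.1 sets no condition of being alive with a graft at Month 6 or 12, so its summaries share the fault.

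A reader might also extend the point to items 10 and 11 of SAP 7.1, which summarise immune cell phenotypes and urinary proteins "by acute rejection status (subjects experiencing at least one acute rejection vs those without any acute rejection"). The inference would be that samples taken after anti-rejection treatment are mixed in. That cannot be established. The detailed biomarker text and schedule rows are redacted, so a sample-timing rule or a split by arm cannot be excluded. No biomarker claim is made here.

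**Conclusion.** The point holds for the survival summary in SAP 7.6.2.1 and items 4c and 8d of SAP 7.1. Grouping by ever versus never CSBPAR over the outcome window puts losses that precede any rejection into the non-rejector group. Under no true effect this produces a gap of about 1 point with constant hazard and early rejections, and about 4 points or more when losses are concentrated early or rejections are spread over 24 months. These sizes rest on assumed event rates and timing, and on independence of rejection and loss.

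A reader might conclude that the planned table will show rejection as protective. The documents do not support that either. The unknown-status rule in SAP 8.3 works against rejectors by an amount that depends on loss to follow-up, so the net direction is undetermined. Two biases of opposite sign and unknown size are a reason to correct the table; they cannot be assumed to cancel.

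**What to change.** In SAP 7.6.2.1, and in items 4c and 8d of SAP 7.1, keep the 5-event condition and replace the grouping. Classify subjects by CSBPAR status at Month 6, only among those alive with a functioning graft at that time, and summarise death or graft loss from there to Month 24. Repeat with status at Month 12. Put earlier losses in the existing listing, marked as before the landmark. Restoring the wording of protocol 8.4.2.1 unchanged would not be enough, because it lacks the at-risk restriction.

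The cost is a change of SAP text using data already collected. A few early losses leave the comparison, and the table remains sparse and descriptive.

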7.6.2.2 Composite Endpoints of CSBP, Death, or Graft Loss

The composite endpoints of CSBP, death, or graft loss will be analyzed only if there is at least one CSBP and at least one death or graft loss. These analyses will include the proportion of all subjects who experience CSBP, death, or graft loss at 12 and 24 months and a time to event analysis of the composite endpoint of CSBP, death, or graft loss.

7.6.2.3 Renal Function

The following table provides a summary/overview of the analysis performed.

Table 7.6.2.3-1: Overview of Analysis: Renal Function

Renal Function variable	Analysis	Time points for analysis
cGFR using MDRD formula	Descriptive summary of absolute values for each Treatment group	Month 3, 6, 12, 24
	Descriptive summary of change from Month 3 values for each Treatment group	Month 6, 12, 24
	Fixed Effects repeated measure model using Time and Treatment as class variables and Month 3 cGFR as a covariate	Month 6, 12, 24
	Mixed effects using Time as random variable and Treatment as class variable. Analysis on absolute cGFR value using Month 3 cGFR as a covariate	Month 6, 12, 24
Urine protein/ creatinine ratio (U _{PR} /CR)	Descriptive summary of absolute values for each treatment group	Month 3, 6, 12, 24
	Descriptive summary of change from Month 3 values for each Treatment group	Month 6, 12, 24
	Fixed Effects repeated measure model using Time and Treatment as class variables and Month 3 cGFR as a covariate	Month 6, 12, 24

cGFR

Calculated GFR at Months 3, 6, 12, and 24 and change in cGFR from Month 3 to Months 6, 12 and 24, respectively, will be descriptively summarized.

A linear mixed effects model will be used to analyze changes from Month 3 cGFR. The linear mixed model for repeated measures with terms of Month 3 cGFR values, treatment, month, and interaction of treatment by month. The variable month will be categorical. The unstructured (UN) covariance structure will be assumed. If computation convergence becomes an issue, the compound symmetric (CS) covariance structure will be used. For each time point, the difference between treatment arms will be calculated along with the corresponding 95% confidence intervals.

Population-mean slopes will be estimated for each treatment group. In addition, the 95% confidence intervals will also be obtained for each mean slope. Intercepts will be summarized in the same manner. This analysis will be based on a linear mixed model including terms for treatment, Month 3 cGFR, treatment-by-month interaction as well as month (continuous covariate) as fixed effects. The model will also include a random intercept and slope for month. Unstructured covariance structure will be used.

For all of the analyses above, for any subject who has one or more missing values for cGFR due to a graft loss or death, the missing values will be imputed as “zero”.

Urine Protein/Creatinine Ratio

Urinary protein to creatinine ratios, to be obtained from single-voided urine specimens at 3, 6, 12 and 24 months post-transplant, will be descriptively summarized.

A linear mixed effects model will be used to analyze changes from Month 3 UPCR. The linear mixed model for repeated measures with terms of Month 3 UPCR values, treatment, month, and interaction of treatment by month. The variable month will be categorical. The unstructured (UN) covariance structure will be assumed. If computation convergence becomes an issue, the compound symmetric (CS) covariance structure will be used. For each time point, the difference between treatment arms will be calculated along with the corresponding 95% confidence intervals.

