#### **8.4.2.3    *Renal Function***

Calculated GFR at Months 3, 6, 12, and 24 and change in cGFR from Month 3 to Months 6, 12 and 24, respectively, will be descriptively summarized. For a subject who has one or more missing values for cGFR due to a graft loss or death, the missing values will be imputed as “zero”.

A linear mixed effects model will be used to analyze changes from Month 3 cGFR. Details of the analyses will be available in the Statistical Analysis Plan.

Population-mean slopes will be estimated for each treatment group. In addition, the 95% confidence intervals will also be obtained for each mean slope. Intercepts will be summarized in the same manner.

In addition, urinary protein to creatinine ratios, to be obtained from single-voided urine specimens at 3, 6, 12 and 24 months post-transplant, will be descriptively summarized.

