5 SAMPLE SIZE AND POWER

This study is descriptive in nature and is not powered to show statistically significant treatment differences for any outcome measure. A sample of approximately 70 subjects, randomized in a 1:1 ratio to the belatacept + EVL and TAC + MMF groups, is planned.

If the true probability of CSBPAR in the belatacept + EVL treatment group is 3.8%, a sample size of 35 subjects allows the estimation of the population proportion (π) with a 95% CI[†] of 0.2% to 16.4% around the observed proportion of CSBPAR. If the rate is 3%, in the TAC +MMF treatment group, then the 95% CI[†] around the estimate would be 0.1% to 15.1%, for lower and upper limits, respectively.

For the secondary endpoint of assessing the difference in the incidence of CSBPAR at 6 months post-transplantation between the TAC + MMF and belatacept + EVL groups, respectively, with 35 subjects per treatment group, if the observed incidences of CSBPAR (conservatively based on study IM103034) are 3% and 3.8%, the 2-sided 95% confidence interval (CI)* of the differences between the observed incidence rates can be summarized as in Table 5-1:

Table 5-1: Confidence Intervals* for the Difference between Two Proportions

Difference of Treatments (assumed proportions)	Lower 95% Confidence Limit	Upper 95% Confidence Limit	Half Width
TAC + MMF (3%)			
vs.	-13.2%	11.3%	12.25%
Bela + EVL (3.8%)			

[†] Confidence Interval Method: Clopper-Pearson

* Confidence Interval Method Score (Wilson)

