7.2 General Methods

All analyses of efficacy and safety endpoints will be summarized descriptively by the two treatment groups. No statistical tests will be performed.

Randomization to the study will be stratified by site only. Any within-treatment confidence interval (CI) for the proportion analyses will be computed using normal approximation, if the number of the events in that treatment group is at least 5. Otherwise, a CI calculated using an exact method will be provided. Any between-treatment CI for the proportion difference analyses will also be computed using normal approximation, if the number of the events in each individual treatment group is at least 5. Otherwise, a CI using an exact method will be provided.

For time to event analyses, if a patient does not experience an event, the censoring will be done at the last follow-up date if the subject discontinues prematurely; otherwise, censoring will be

done at the last dose date if the subject completed the 24 month-treatment period, unless specified otherwise.

The following table provides an overview of the primary and key secondary analyses to be performed.

Table 7.2-1: Overview of Primary and Key Secondary Analyses

Measure of Interest	Analysis Method
Proportion of subjects who experience a CSBPAR at 6, 12 and 24 months post-transplant	Point estimate of the proportion and 95% CI [*] within each treatment group at 6 months.
Difference in the incidence of CSBPAR between arms, at 6, 12 and 24 months post-transplant	Point estimate and 95% CI [†] for the difference between the two arms
Time to first CSBPAR	Kaplan-Meier (KM) estimates of survival functions. Hazard Ratio and 95% CI [§]
Proportion of Subjects who survive with a functioning graft at 24 months post-transplant	Point estimate of the proportion and 95% CI [*] within each treatment group at 24 months (to be produced if there are at least 5 subjects across treatment groups who died or experienced graft loss)
Time to death or graft loss	KM estimate of subject and graft survival Hazard Ratio and 95%CI [§] (to be produced if there are at least 5 subjects across treatment groups who died or experienced graft loss)

* Confidence Interval Formula: Exact (Clopper-Pearson)

† Confidence Interval Method: Score (Wilson)

§ Using Cox Proportional Hazard model

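### The SAP names two different covariates for the UPCR repeated-measures model: Month 3 cGFR in Table 7.6.2.3-1 and Month 3 UPCR in the text

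*SAP*

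**What the plan says.** SAP 7.6.2.3 describes the UPCR model twice.

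- **Table 7.6.2.3-1, last row, under urine protein/creatinine ratio:** "Fixed Effects repeated measure model using Time and Treatment as class variables and Month 3 cGFR as a covariate", at Months 6, 12 and 24. The row names no response variable and no treatment-by-month term. The identical sentence appears higher in the table under cGFR.
- **Text under Urine Protein/Creatinine Ratio:** "A linear mixed effects model will be used to analyze changes from Month 3 UPCR". The terms follow: "The linear mixed model for repeated measures with terms of Month 3 UPCR values, treatment, month, and interaction of treatment by month". The text also gives a covariance structure with a fallback, and the output: "For each time point, the difference between treatment arms will be calculated along with the corresponding 95% confidence intervals".

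For cGFR, table and text agree on the covariate. The cGFR text reads "The linear mixed model for repeated measures with terms of Month 3 cGFR values, treatment, month, and interaction of treatment by month".

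Nothing else settles the UPCR covariate. SAP 7.1, which lists modifications and clarifications, does not mention it. Protocol 8.4.2.3 plans only a descriptive summary of UPCR, so it contains no model to fall back on.

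**The concern.** UPCR is a listed secondary endpoint (Protocol 8.3.2, SAP 4.2), and this model is the only planned source of an arm difference in UPCR with a confidence interval. The covariate changes both the estimate and the interval. An SAP should leave one specification for each analysis. Here it leaves two, in an open-label study, with no rule on whether table or text governs.

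The table version also makes little sense as a deliberate choice. It would adjust UPCR for the Month 3 value of another variable and omit a term for the Month 3 value of UPCR itself, which is usually the stronger predictor of later UPCR. The cGFR model adjusts for its own Month 3 value, and the UPCR text follows the same pattern.

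**Working it through.** **1. Side by side**

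| Model | Covariate in table | Covariate in text |
|---|---|---|
| cGFR | Month 3 cGFR | Month 3 cGFR |
| UPCR | Month 3 cGFR | Month 3 UPCR |

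Only the UPCR table cell departs from the pattern, and its wording is identical to that of the cGFR row. A copied row is the likely cause. Both table rows omit the treatment-by-month term that both texts include, so that omission looks like brevity in an overview. The covariate is a direct conflict.

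**2. Figures to reproduce.** None. No sample size, power or event count in the documents depends on this covariate.

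**3. Illustration of precision.** Inputs:

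- n = 35 per arm, from SAP section 5: "A sample of approximately 70 subjects, randomized in a 1:1 ratio to the belatacept + EVL and TAC + MMF groups, is planned".
- r, the correlation between Month 3 and later UPCR. It is not in the documents and is assumed to be 0.3, 0.5 or 0.7.
- One time point, equal variances (SD = 1), Month 3 UPCR balanced between arms, and Month 3 cGFR explaining little of UPCR. All are assumptions.

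Per-subject variance of a change score without the Month 3 UPCR term: 2(1−r). With the term: 1−r² = (1−r)(1+r). The SE ratio is therefore sqrt(2(1−r)/(1−r²)) = sqrt(2/(1+r)).

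The 95% half-width for the arm difference is 1.96 × sqrt(variance × 2/35), in SD units.

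| r | Variance without | Variance with | SE ratio | Half-width without | Half-width with |
|---|---|---|---|---|---|
| 0.3 | 1.40 | 0.91 | 1.24 | 0.554 | 0.447 |
| 0.5 | 1.00 | 0.75 | 1.15 | 0.469 | 0.406 |
| 0.7 | 0.60 | 0.51 | 1.08 | 0.363 | 0.335 |

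**4. The response matters only in the table version.** With Month 3 UPCR as a covariate, modelling change or the absolute value gives the same arm difference, because subtracting the Month 3 value only moves its coefficient by one. Without that covariate the two differ. If the table row meant absolute UPCR, the variance without the term would be 1 and the SE ratio 1/sqrt(1−r²):

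- r = 0.3: 1/sqrt(0.91) = 1.05
- r = 0.5: 1/sqrt(0.75) = 1.15
- r = 0.7: 1/sqrt(0.51) = 1.40

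**5. The point estimates also differ.** Suppose the arms differ by d in Month 3 UPCR. Under the same simple model, the change-score estimate differs from the adjusted one by −(1−r)d, and an absolute-value estimate differs from it by +rd. With an assumed d of 0.25 SD:

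| r | Change score | Absolute value |
|---|---|---|
| 0.3 | −0.175 SD | +0.075 SD |
| 0.5 | −0.125 SD | +0.125 SD |
| 0.7 | −0.075 SD | +0.175 SD |

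These are gaps between two specifications, not measures of bias.

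**The case against.** The strongest reply is that this is a clerical slip with little riding on it. The table calls itself an overview. For UPCR it gives no response, no interaction and no covariance structure, so a programmer would need the text, and the text names Month 3 UPCR. The study is descriptive, and SAP 7.2 states "No statistical tests will be performed". Absolute UPCR and its change from Month 3 are also summarised by arm whichever model is run. All of this stands, and it limits the importance of the point. It does not remove the contradiction, because the SAP nowhere gives the text precedence.

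Three stronger readings are tempting, and the documents do not support them.

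- **A chance baseline imbalance would bias the table version through regression to the mean.** Month 3 is about 12 weeks after assigned treatment starts (Protocol 4.3), so an arm difference there may be a treatment effect. The pre-transplant urine sample is taken at screening (Protocol Table 5.1-1), and neither version adjusts for it.
- **The table version models change with no account of Month 3 UPCR.** The row names no response. If change is meant, the Month 3 value is still subtracted. What is missing is its covariate term.
- **The table version costs a fixed share of subjects, say 15% to 25%.** That is 1−(1+r)/2 at r = 0.7 and 0.5. It rests on correlations the documents do not give, on a change-score response, and on a one-time-point formula, whereas the plan is a repeated-measures model over three time points.

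**Conclusion.** The conflict is real and unresolved: one secondary analysis has two covariates. The choice changes the between-arm UPCR estimate and its 95% interval. If the table row were followed with a change-score response, the standard error would be larger by a factor of about 1.24, 1.15 or 1.08 at r = 0.3, 0.5 or 0.7, under the assumptions in step 3 of the working. These factors are illustrations, not predictions for this trial. The text is the fuller specification and the likelier basis for programming, so the practical risk is modest. It is confined to one secondary endpoint and leaves the primary endpoint, the sample size and any conclusion on rejection untouched. The point is worth correcting because the SAP is the only source for this model.

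**What to change.** In the UPCR model row of Table 7.6.2.3-1, replace Month 3 cGFR with Month 3 UPCR. In the same row, state the response (change from Month 3 UPCR) and add the treatment-by-month interaction, so that the row describes the model in the text. If a cGFR covariate was intended, the sponsor should say so, give the reason and amend the text instead. The cost is an edit to one table row. No data collection, sample size or other analysis changes.
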